8.7.1.2 Categories for Adverse Event Assessment

All AEs will be assessed and documented by the investigator according to the categories detailed below.

Seriousness

For each AE, the seriousness must be determined according to the criteria given in [Section 8.7.1.5](#).

Severity

The intensity of an AE is classified according to the following categories, taking into account the possible range of the intensity of the event:

- Mild The adverse event is transient and easily tolerated by the subject.
- Moderate The adverse event causes the subject discomfort and interrupts the subject's usual activities

- **Severe** The adverse event causes considerable interference with the subject's usual activities and may be incapacitating or life-threatening.

Specific drug treatment

Any specific drug treatment will be documented.

Causal relationships to investigational product and dye

The investigator will use the following definitions to assess the relationship of the adverse event to the use of investigational product:

Definitely related: Event can be fully explained by administration of the investigational product.

Probably related: Event is most likely to be explained by administration of the investigational product rather than the subject's clinical state or other agents/therapies.

Possibly related: Event may be explained by administration of the investigational product or by the subject's clinical state or other agents/therapies.

Probably not related: Event is most likely to be explained by the subject's clinical state or other agents/therapies, rather than the investigational product.

Definitely not related: Event can be fully explained by the subject's clinical state or other agents/therapies.

For causality assessments, events meeting the categories of definitely, probably, or possibly related will be considered to be related to investigational product.

Causal relationship to study procedure

The investigator will use the following definitions to assess the relationship of the adverse event to the study procedure:

Definitely related: Event can be fully explained by the study procedure.

Probably related: Event is most likely to be explained by the study rather than the subject's clinical state or other agents/therapies.

Possibly related: Event may be explained by the study procedure or by the subject's clinical state or other agents/therapies.

Probably not related: Event is most likely to be explained by the subject's clinical state or other agents/therapies, rather than the study procedure.

Definitely not related: Event can be fully explained by the subject's clinical state or other agents/therapies.

For causality assessments, events meeting the categories of definitely, probably, or possibly related will be considered to be related to the study procedure.

8.7.1.3 Assessments and Documentation of Adverse Events

Any AE (observed, volunteered, or elicited) should be recorded in detail in the source documentation.

The following information is required:

- The date and time of onset of any AE
- The date and time the AE ends
- The seriousness of the AE will be assessed by the investigator. If the investigator deems that an AE qualifies as an SAE, a special form provided by the sponsor should be completed and the event must be immediately reported to the sponsor. A definition of serious adverse events is provided below.
- The maximum intensity (mild, moderate, or severe)
- Whether drug treatment was administered for the event
- The relationship of the AE to the investigational product, dye and to study conduct (for definitions, see above)
- Did the AE cause study discontinuation
- The outcome of the AE (Resolved, Resolved with sequelae, Ongoing, Unknown, Lost to Follow-up, Death)

AEs will be coded according to an internationally recognized dictionary (Medical Dictionary for Regulatory Activities or MedDRA).

8.7.1.4 Expected Adverse Events

Expected Conduct-Related AEs

AEs are determined by the investigator. If in the investigator's opinion/experience an event is expected and not uncommon for that surgery (i.e., nausea in the recovery room), and it is not deemed different in severity from other episodes observed in the same situation, then it is up to the investigator's discretion to determine the event to be adverse.

An example of an expected conduct-related event is postoperative pain at the site of the incision.

[REDACTED]

[REDACTED]

[REDACTED]

Precautionary Measures

Special precautionary measures are not considered to be necessary for this study. In case of emergency, standard emergency procedures will be employed.

Unexpected Adverse Events

An unexpected adverse event is defined as an adverse reaction that in nature and severity is not consistent with the applicable product information (e.g., Investigator's Brochure).

Any adverse experience that is not listed in the current Investigator's Brochure or which is, with regard to the specificity or severity, not consistent with the risk information shall be regarded as unexpected.

Examples would be (a) acute renal failure listed in the Investigator's Brochure with a subsequent new report of interstitial nephritis and (b) hepatitis with a first report of fulminant hepatitis. "Unexpected" as used in this definition refers to an adverse drug experience that has not been previously observed and included in the product information, rather than from the perspective of such experience not being anticipated from the pharmacological properties of the investigational product.

8.7.1.5 Serious Adverse Events

Definition of Serious Adverse Events

Definition

The following SAE definition is based on ICH guidelines and the final rule issued by the Food and Drug Administration (FDA) and effective 06 Apr 1998. It is to be applied to AEs (defined in [Section 8.7.1.1](#)).

An SAE is classified as any untoward medical occurrence that at any dose

- results in death, or
- is life threatening, or
- requires inpatient hospitalization or prolongation of existing hospitalization, or

- results in persistent or significant disability/incapacity, or
- is a congenital anomaly/birth defect, or
- is an important medical event (see paragraphs below).

The term 'life threatening' in the definition refers to an event in which the subject was at risk of death at the time of the event; it does not refer to an event that hypothetically might have caused death if it were more severe.

Medical and scientific judgment should be exercised in deciding whether it is appropriate to report an AE as serious also in other situations, such as important medical events that may not be immediately life threatening or result in death or hospitalization but may jeopardize the subject or may require intervention to prevent one of the other outcomes listed in the definition above. These should also usually be considered serious. Examples of such events are intensive treatment in an emergency room or at home for allergic bronchospasm or blood dyscrasias or convulsions that do not result in subject hospitalization.

Hospitalizations for planned elective surgeries will not be considered serious adverse events.

Actions and reporting obligations in case of serious adverse events

The investigator should take appropriate diagnostic and therapeutic measures to minimize the risk to the subject. If any SAE occurs over the course of the study, investigators or other site personnel will inform Navidea Biopharmaceutical representatives within one day (i.e., within 24 hours) of becoming aware of the SAE. [REDACTED]

[REDACTED]. For fatal or life-threatening adverse events where important or relevant information is missing, active follow-up is undertaken immediately.

Pregnancy will have the same time reporting obligations to the sponsor as SAEs. Upon notification, Navidea will provide a form for collection of pregnancy information.

All SAEs must also be recorded on the Adverse Event eCRFs.

Notification of the IECs/IRBs

The sponsor and/or the investigator will notify the IECs/IRBs about all relevant events (e.g., Serious Adverse Events [SAEs] and Suspected, Unexpected, Serious Adverse Reactions [SUSARs]) according to all applicable regulations.

Notification of the authorities

The sponsor will process and report all relevant events (e.g., SAEs, SUSARs) to the authorities according to all applicable regulations.

Sponsor's notification of the investigators

The sponsor will inform all investigators about reported relevant events (e.g., SAEs, SUSARs) according to all applicable regulations.

8.7.2 Further Safety Assessments

8.7.2.1 Physical Examination

Complete physical examinations will be conducted according to the Schedule of Study Events (see [Appendix 1](#)).

Physical examination will be performed for the following body systems:

- General appearance
- Skin/dermatological
- Eyes, ears, nose, throat
- Head and neck (including thyroid)
- Lungs
- Heart
- Abdomen (liver, kidney, spleen, gastrointestinal)
- Pelvis
- Lymph nodes
- Musculoskeletal
- Nervous system

8.7.2.2 Vital Signs

Vital signs comprise the measurement of systolic and diastolic blood pressure, respiration, and heart rate. All vital signs will be measured after the subject has been in a resting position for at least 1 minute. Heart rate should be measured immediately before or immediately after blood pressure measurement.

Vital signs will be measured at screening, baseline (0-10 minutes before investigational product injection), 10 ± 3 , 30 ± 3 , 60 ± 5 minutes post injection, and after scanning.

Any clinically significant change from baseline that results in a change in subject management will be considered an AE.

8.8 Other Procedures and Variables

8.8.1 Blood Sampling

8.8.2 Laboratory Data for Subject Characterization

Clinical laboratory tests to be evaluated in this study include hematology (complete blood count) and serum chemistry (basic metabolic panel). Blood samples will be obtained only at screening in accordance with the Schedule of Events. Table 4 shows the minimum parameters to be assessed:

Table 4. Minimum Clinical Laboratory Parameters

Hematology	hemoglobin (Hb), platelets, white blood cell (WBC)
Serum chemistry	creatinine, chloride, potassium, sodium, carbon dioxide (CO2)/bicarbonate, blood urea nitrogen (BUN)

All laboratory reports must be promptly reviewed for clinical significance by the investigator, and upon review, initialed and dated by the investigator.

Good clinical practice would suggest that a copy of the safety laboratory results be available to the subject and to the subject's referring physician.

The expected amount of blood to be withdrawn is shown in Table 5.

Table 5. Approximate Amount of Blood Withdrawn

	mLs
Chemistry	5
Hematology	4
Total	9

9 STATISTICAL METHODS

9.1 Introduction

This study is a prospective, open-label study conducted at approximately 4 to 6 study centers in the US. The objectives of the statistical analyses are to establish the safety and efficacy of Lymphoseek in targeting lymphoid tissue in subjects with cervical cancer who are undergoing lymph node mapping.

A study center is defined as a treatment administration site or group of treatment administration sites under the control and supervision the same Primary Investigator.

9.2 Randomization Methods

There is no randomization planned for this study. All enrolled subjects will receive Lymphoseek along with an optional administration of either VBD or ICG.

9.3 Pooling of Study Centers

There will be no selective pooling of study centers. Subjects from all study centers will be pooled for the analysis.

9.4 Efficacy Variables

9.4.1 Primary Efficacy Variables

The primary efficacy variable is the per subject false negative rate (FNR), which is the number of subjects with pathologically negative Lymphoseek-identified SLN(s) (or no SLNs were detected) and at least one pathologically positive non-SLN divided by the number of subjects with at least one pathologically positive node (SLN or non-SLN)

9.4.2 Secondary Efficacy Variables

The secondary efficacy variables are the following:

- Per-subject sensitivity, defined as the number of subjects with at least one pathologically positive SLN divided by the number of subjects with at least one pathologically positive node (SLN or non-SLN)
- Per-subject negative predictive value (NPV), defined as the number of subjects with no pathologically positive lymph nodes (SLNs or non-SLNs) divided by the number of subjects with pathologically negative Lymphoseek-identified SLN(s) (or no SLNs were detected)
- Per-subject accuracy, defined as the proportion of subjects whose lymph nodes were either all pathologically negative (i.e, true negative subject) or at least one SLN was

pathologically positive (i.e., true positive subject) divided by the number of subjects in the analysis population

- Rate of tumor detection in SLNs, defined as the proportion of subjects with at least one pathologically positive SLN divided by the number of subjects in the analysis population
- Rate of tumor detection in non-SLNs, defined as the proportion of subjects with at least one pathologically positive non-SLN divided by the number of subjects in the analysis population
- Nodal concordance, defined as the proportion of lymph nodes identified intraoperatively by dye (e.g., VBD or ICG) that are also identified intraoperatively by Lymphoseek
- Subject concordance, defined as the number of subjects whose lymph nodes that were identified intraoperatively by dye were also all identified intraoperatively by Lymphoseek
- Reverse nodal concordance, defined as the proportion of lymph nodes identified intraoperatively by Lymphoseek that are also identified intraoperatively by dye
- Subject reverse concordance, defined as the number of subjects whose lymph nodes that were identified intraoperatively by Lymphoseek were also all identified intraoperatively by dye
- Number of SLNs per subject
- Number of lymph nodes identified intraoperatively by dye
- Number and anatomical locations of lymph nodes identified by preoperative Lymphoscintigraphy

9.5 Pharmacokinetic Variables

Not applicable.

9.6 Safety Variables

9.6.1 Primary Safety Variables

The primary safety variables for this study are:

- Vital signs (screening, at pre- and 10, 30 and 60 minutes post-injection timepoints)
- Adverse events

9.7 Sample Size Justification

Approximately 40 subjects diagnosed with cervical cancer will be enrolled in the study. This sample size was chosen in order to provide exploratory results for the primary endpoint of per subject FNR within this subject population. This study is not powered with respect to testing any statistical hypotheses.

It is anticipated that approximately 20% of the enrolled subjects will have at least one pathologically positive node, resulting in a total of 8 subjects available for the primary endpoint analysis. With an expected FNR of 12.5%, i.e., 1 false negative subject, a sample size of 8 subjects will allow for an exact 95% confidence interval half-width of 26% on the true subject FNR. Due to the asymmetric nature of the exact binomial confidence interval, the half-width described in this protocol is simply half the entire width of the confidence interval and not the distance between the estimate and the confidence limits.

9.8 Handling of Missing Data

There will be no missing value imputation used in this study. All endpoints will be analyzed with subjects who have non-missing data (i.e., a complete case analysis).

9.9 Statistical Analysis

9.9.1 Analysis Populations

The following analysis populations will be defined:

Intent-to-treat (ITT): The ITT population will include all enrolled subjects with administration of test medicine for whom at least one lymph node was removed with histopathology available.

Per protocol (PP): The PP population will include all ITT subjects without major protocol violations.

Safety: The safety population will include all enrolled subjects with administration of test medicine.

The analysis of the efficacy endpoints will be conducted on ITT and PP populations. The primary analysis set will be the ITT analysis set. All safety analyses will be conducted on the safety population.

9.9.2 Analysis of Baseline and Demographic Characteristics

Baseline and demographic characteristics will be summarized for all subjects in the safety population. Continuous variables will be displayed via summary statistics (mean, median, sample size, standard deviation, minimum, and maximum). Categorical variables will be summarized via counts and percentages.

9.9.3 Analysis of Primary Efficacy Variables

The per-subject FNR will be computed as follows using all ITT subjects with at least one pathologically positive lymph node:

$$FNR_{\text{subj}} = \frac{\text{Subjects with at least one pathologically positive non-SLN and no pathologically positive SLNs (i.e., false negative subject)}}{\text{Subjects with at least one pathologically positive node (SLN or non-SLN)}}$$

Along with reporting the number of false negative subjects and the observed per-subject FNR, an exact two-sided 95% confidence interval will be computed.

The above analyses will be repeated using the PP analysis population.

9.9.4 Analysis of Secondary Efficacy Variables

The per-subject sensitivity will be computed as follows using all ITT subjects with at least one pathologically positive lymph node:

$$SENS_{\text{subj}} = \frac{\text{Subjects with at least one pathologically positive SLN (i.e., true positive subject)}}{\text{Subjects with at least one pathologically positive node (SLN or non-SLN)}}$$

Along with reporting the number of true positive subjects and the observed per-subject sensitivity, an exact two-sided 95% confidence interval will be computed.

The per-subject NPV will be computed as follows using all ITT subjects with pathologically negative Lymphoseek-identified SLN(s) (or no SLNs were detected):

$$NPV_{\text{subj}} = \frac{\text{Subjects with no pathologically positive nodes (SLNs and non-SLNs) (i.e., correctly predicted negative subjects)}}{\text{Subjects with no pathologically positive SLNs or subjects with no SLNs}}$$

Along with reporting the number of correctly predicted negative subjects and the observed per-subject NPV, an exact two-sided 95% confidence interval will be computed.

The per-subject accuracy will be computed as follows using all ITT subjects:

$$\frac{\text{Subjects whose lymph nodes were either all pathologically negative (i.e., true negative subjects) or subjects with at least one pathologically positive SLN}}$$

$$ACC_{subj} = \frac{\text{(i.e., true positive subjects)}}{\text{All ITT subjects}}$$

Along with reporting the total number of true negative and true positive subjects and the observed per-subject accuracy, an exact two-sided 95% confidence interval will be computed.

The rate of tumor detection in SLNs will be computed as follows using all ITT subjects:

$$\text{Rate of SLN Tumor Detection} = \frac{\text{Subjects with at least one pathologically positive SLN}}{\text{All ITT subjects}}$$

Along with reporting the total number of subjects with at least one pathologically positive SLN and the observed rate of SLN tumor detection, an exact two-sided 95% confidence interval will be computed.

The rate of tumor detection in non-SLNs will be computed as follows using all ITT subjects:

$$\text{Rate of SLN Tumor Detection} = \frac{\text{Subjects with at least one pathologically positive non-SLN}}{\text{All ITT subjects}}$$

Along with reporting the total number of subjects with at least one pathologically positive non-SLN and the observed rate of non-SLN tumor detection, an exact two-sided 95% confidence interval will be computed

The nodal concordance, P_1 , will be computed as follows using lymph nodes from all subjects in the ITT population:

$$P_1 = \frac{\text{Number of SLNs identified intraoperatively by VBD or ICG}}{\text{Number of lymph nodes identified intraoperatively by VBD or ICG}}$$

9.9.4.1 Along with reporting the number of SLNs identified intraoperatively by VBD or ICG and the observed nodal concordance, an exact two-sided 95% confidence interval will be computed.

The subject concordance, P_2 , will be computed as follows using all subjects in the ITT population:

$$P_2 = \frac{\text{Subjects whose lymph nodes that were intraoperatively identified by VBD or ICG were also all identified by Lymphoseek}}{\text{Subjects with at least one lymph node intraoperatively identified by VBD or ICG}}$$

Along with reporting the number of subjects in the numerator and the observed subject concordance, an exact two-sided 95% confidence interval will be computed.

The reverse nodal concordance, P_3 , will be computed as follows using lymph nodes from all subjects in the ITT population:

$$P_3 = \frac{\text{Number of SLNs identified intraoperatively by VBD or ICG}}{\text{Number of SLNs}}$$

Along with reporting the number of SLNs identified intraoperatively by VBD or ICG and the observed reverse nodal concordance, an exact two-sided 95% confidence interval will be computed.

The subject reverse concordance, P_4 , will be computed as follows using all subjects in the ITT population:

$$P_4 = \frac{\text{Subjects whose SLNs were also all identified by VBD or ICG}}{\text{Subjects with at least one SLN}}$$

Along with reporting the number of subjects in the numerator and the observed reverse subject concordance, an exact two-sided 95% confidence interval will be computed.

The average number of SLNs per subject will be computed, along with a 95% confidence interval.

The average number of lymph nodes identified intraoperatively by dye per subject will be computed, along with a 95% confidence interval.

The average number of lymph nodes identified by preoperative Lymphoscintigraphy per subject will be computed, along with a 95% confidence interval.

The number and percent of lymph nodes identified by preoperative Lymphoscintigraphy will be reported per anatomical location.

The above analyses of secondary variables will be repeated using the PP analysis population.

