8.4.2 Lymphoseek-Designated “Hot” Nodes

Room Background Count

Using the handheld gamma detection system a room background shall be determined by recording three 2-second counts or one 10-second count obtained at least 30 cm away from the injected subject and any other radiation source.

Normal Tissue Background Count

Using the handheld gamma detection system, identify an anatomical region greater than 30 cm from the Lymphoseek injection site and not over the abdomen. A set of three 2-second counts or one 10-second count on non-lymphoid tissue (background counts) are obtained to set the threshold criteria.

In Vivo

Lymphoseek positivity is based on radioactivity counts derived from the application of the handheld gamma probe *in vivo*, where such counts must satisfy the threshold criterion of greater than the quantity of 3 times the square root of the mean normal tissue background count (i.e., standard deviation) added to the mean normal tissue background count (referred to as the “ 3σ rule”). Any nodal count NOT meeting this threshold criterion will be considered a negative finding (not localized). Use [Appendix 2](#) to assist in determining the 3σ level from the normal tissue background level.

Ex Vivo

Lymphoseek positivity is based on radioactivity counts derived from the application of the handheld gamma probe *ex vivo* (excised from the subject), where such counts must satisfy the threshold criterion of greater than the quantity of 3 times the square root of the mean normal tissue background count (i.e., standard deviation) added to the mean normal tissue background count (referred to as the “ 3σ rule”). Any nodal count NOT meeting this threshold criterion will be considered a negative finding (not localized). Use Appendix 2 to assist in determining the 3σ level from the normal room background level.

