negative or no counts (not hot)	positive (hot)	Comment on why lymph node was removed. Send to pathology for further evaluation.
Dye Status		
dye-identified node	N/A	ANY dye-identified node is sent to pathology for further evaluation regardless of radioactive status.

6. A thorough evaluation of the remaining lymphatic basin should be undertaken since more than one LN may be found. This evaluation should include a combination of palpation, visualization, and gamma detector survey for evidence of dye and/or increased gamma detector count rates.
7. Probing of the area will be complete when all selected node counts are negative by use of the threshold criterion. The surgeon will continue with visualization and palpation according to local practice to ensure that no grossly positive LNs remain at the site of resection.

If a subject has neither a dye-identified node nor any “hot” nodes, continue with visualization and palpation according to your medical expertise.

Pelvic lymphadenectomy will be performed in accordance with institutional standards. Additional surgical intervention such as radical hysterectomy should be performed in accordance with the subject’s surgical plan and the discretion of the surgeon.

All removed LNs (SLNs and NSLNs) must be sent to pathology for using the minimum requirements of histopathological evaluation outlined in the trial pathology manual.

For the purposes of analysis, a sentinel lymph node is defined as being hot ex vivo (lymph nodes with counts above the 3σ rule threshold).

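### The exact confidence intervals for nodal concordance (P1) and reverse nodal concordance (P3) treat nodes from one subject as independent and can be too narrow; the P3 and P4 denominators also leave subjects without dye unresolved

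*Combined protocol and SAP*

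**What the plan says.** Section 9.9.4 defines four measures of agreement between Lymphoseek and dye.

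- **P1, nodal concordance.** Sentinel nodes (SLNs) identified by dye, divided by all nodes identified by dye. It "will be computed as follows using lymph nodes from all subjects in the ITT population". The interval is given under the number 9.9.4.1: with "the observed nodal concordance, an exact two-sided 95% confidence interval will be computed".
- **P3, reverse nodal concordance.** The same numerator, divided by all SLNs: "The reverse nodal concordance, P_3 , will be computed as follows using lymph nodes from all subjects in the ITT population". Again, with "the observed reverse nodal concordance, an exact two-sided 95% confidence interval will be computed".
- **P2 and P4.** Subject-level versions, which ask whether all of a subject's nodes agree. P2 is taken over subjects with at least one dye-identified node, P4 over subjects with at least one SLN. Both have exact 95% intervals.

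The node-level intervals recur in the per-protocol (PP) set: "The above analyses of secondary variables will be repeated using the PP analysis population".

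The only explanation of the word exact is in section 9.7, which refers to the "asymmetric nature of the exact binomial confidence interval". That sentence concerns the FNR interval, but it is also the natural reading for a ratio of node counts.

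Three other provisions matter:

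- Section 8.4.3, step 6, expects several nodes in some subjects: "A thorough evaluation of the remaining lymphatic basin should be undertaken since more than one LN may be found".
- Section 8.4.2 bases the positivity threshold on the subject's own background: "A set of three 2-second counts or one 10-second count on non-lymphoid tissue (background counts) are obtained to set the threshold criteria".
- Sections 5.3 and 9.2 make dye optional, while section 9.8 prescribes a complete-case analysis without imputation.

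**The concern.** A binomial interval is valid for independent trials. Here the sampling unit is the subject, and the nodes of one subject have common causes of agreement or disagreement: the same tracer administration, the same background-based threshold, the same dye procedure if one was used, and the same operation. If outcomes are positively correlated within subjects, the pooled node count overstates the information and the interval is too narrow. Section 9 contains no robust variance, design effect, subject-level resampling or other adjustment. It mentions a Statistical Analysis Plan document only for additional safety analyses (9.9.5).

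What is at stake is the stated precision of two secondary objectives. The study tests no hypothesis, so estimates with intervals are its output.

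A second, separate question concerns the denominators. P3 counts all SLNs, and P4 counts all subjects with an SLN, in the ITT population. The plan does not say what happens to subjects who were given no dye.

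**Working it through.** **1. The plan's own precision figure.** None is given for P1 or P3. The one in section 9.7 is for the FNR: 1 false negative among 8 subjects. The Clopper-Pearson 95% interval for 1/8 is 0.32% to 52.65%, so the half-width is (52.65 - 0.32)/2 = 26.2%. The stated 26% reproduces, which confirms that exact means exact binomial there.

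**2. A single example.** From the documents: about 40 subjects. Assumed: 3 nodes in each, concordance 90%, ICC 0.3.

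- Planned interval at 108/120: 83.2% to 94.7%, width 11.5 points.
- Design effect = 1 + (m - 1) x ICC = 1 + 2 x 0.3 = 1.6; effective n = 120/1.6 = 75.
- Clopper-Pearson at 90% with n = 75: 80.9% to 95.7%, width 14.8 points, or 1.29 times as wide.
- Simulated coverage of the planned interval in this setting: about 91%.

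**3. Coverage of the planned P1 interval over a range.** All inputs are assumed: 20 or 40 contributing subjects; nodes per subject 1 + Poisson(m - 1); concordance 80, 90 or 95%; beta-binomial correlation; 20,000 replicates per setting. Each cell gives the range over the six combinations of subjects and concordance.

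| Mean nodes | ICC 0.1 | ICC 0.2 | ICC 0.3 | ICC 0.5 |
|---|---|---|---|---|
| 1.5 | 96.0-98.3% | 95.0-98.0% | 94.3-97.5% | 92.7-96.6% |
| 2 | 95.2-98.0% | 93.5-97.1% | 91.9-96.5% | 88.5-95.1% |
| 3 | 93.3-97.3% | 90.5-95.8% | 87.8-94.5% | 82.2-92.2% |

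With independent nodes (ICC 0) the range is 96.2-98.7%. This built-in conservatism of the exact interval absorbs mild clustering. At a mean of 3 nodes the upper end of each range comes from one setting (20 subjects, concordance 95%). In the other five, coverage is 90.5-92.5% at ICC 0.2 and 82.2-85.2% at ICC 0.5.

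**4. Width.** With unequal node counts the design effect is about 1 + (E[n²]/E[n] - 1) x ICC. For 1 + Poisson(2), E[n] = 3 and E[n²] = 2 + 9 = 11, so the factor is 11/3 - 1 = 2.67.

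- ICC 0.2: 1 + 0.533 = 1.53, square root 1.24.
- ICC 0.5: 1 + 1.333 = 2.33, square root 1.53.

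For 40 subjects and concordance 80% the planned width is 14.9 points. Multiplying gives 18.5 and 22.8 points, in line with the simulated adjusted widths of 18.5 and about 23.

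**5. The P3 and P4 denominators.** The P1 and P2 denominators need at least one dye-identified node, so subjects without dye drop out by construction. The P3 and P4 denominators do not need one. If subjects without dye are kept, and the mean number of SLNs is the same with and without dye, then P3 = (share given dye) x (concordance among those given dye). Assuming a share of 50% and concordance of 90%, P3 = 0.5 x 0.9 = 45%. P4 is scaled down in the same way, because a subject with an SLN but no dye cannot have all her SLNs dye-identified. Section 9.9.4 (all ITT subjects) points towards keeping them; section 9.8 (complete case) points towards dropping them, since they arguably have no dye status.

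**The case against.** The strongest reply is that little depends on this. Sections 3.1 and 9.7 call the study exploratory, no test or threshold is attached to P1 or P3, and the point estimates do not change. Every input to the coverage figures is assumed. At a mean of 1.5 nodes coverage never falls below 92.7%, and at ICC 0.1 never below 93.3%. The plan already reports the mean number of SLNs and of dye-identified nodes per subject, so readers can see the cluster size. All of this stands and keeps the point minor. It does not make the interval right, because its validity rests on an independence that the design gives no reason to expect.

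P2 is a subject-level companion with a suitable interval, but it asks a stricter question (all nodes agree), so it does not replace a correct interval for P1.

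A reader might infer that P3 is much worse off than P1, on the ground that every SLN of a subject without dye is discordant and these nodes cluster by construction. The documents do not support this as a fact. The complete-case rule in section 9.8 may remove those subjects, and then P3 behaves like P1. Even if they stay, the shortfall in coverage depends on whether dye receipt is treated as a random draw or as fixed. On that reading the more basic fault is a diluted estimate, in P4 as well as P3, and a wider interval would not cure it.

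**Conclusion.** The point holds, at minor severity. As written, the P1 and P3 intervals ignore within-subject correlation and can be too narrow. For P1 the loss is slight at about 1.5 nodes per subject or with weak correlation. It becomes material at around 3 nodes with ICC of 0.2 or more (about 91-96% coverage at 0.2, about 82-92% at 0.5), or around 2 nodes with ICC of about 0.3 or more. These figures rest on assumed node counts, correlation and concordance, so they show what can happen, not what will. The same reasoning applies to P3, but no separate coverage figure is claimed for it.

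The treatment of subjects without dye is ambiguous and could dilute both P3 and P4. A reader should not conclude that P4 is safe from this, nor that the primary result is in doubt: the per-subject FNR and P2 are unaffected.

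**What to change.** **Interval.** In section 9.9.4, for P1, P3 and their PP repeats:

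- Keep the pooled point estimates.
- Make the reported 95% interval subject-clustered. Options are an exact interval on an effective sample size, a ratio-estimator (robust) variance, or a bootstrap that resamples subjects. Name one in advance.
- State in advance what is done at 0% or 100% observed concordance, where the within-subject variation cannot be estimated.
- Show the pooled exact interval only as descriptive.

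**Denominator.** State that P3 and P4 are computed among ITT subjects who received dye, and report that number beside them.

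**Cost.** Plan wording and a few lines of code, with no new data. With the effective-sample-size option, P1 intervals are about 3-10% wider if nodes are in fact independent, and up to 59% wider at a mean of 3 nodes with ICC 0.5, where the planned interval under-covers.

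That option needs care at the boundary. If the effective n is set to the number of subjects when agreement is perfect, 40 subjects with 3 nodes each give a lower limit of 91.2% for 120/120 but 95.4% for 119/120. It is therefore one choice among several, not the prescription.
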